8. Applied SOPs.....	14

1. Objective of PMS

To analyze safety and efficacy information on Pergoveris™ in post-marketing uses, as well as factors likely to influence safety and efficacy

Primary objective: To get safety information in subjects using Pergoveris™

- 1) Serious Adverse Event (SAE)
 - ① If causing death or threatening one's life
 - ② If hospitalization or prolonged duration of hospitalization is necessary
 - ③ If causing continuous or significant disability or dysfunction
 - ④ If causing congenital malformation or abnormality
 - ⑤ Other medically critical conditions
- 2) Adverse event/adverse drug reaction unexpected in precautions
- 3) Already known adverse drug reaction
- 4) Non-serious adverse drug reaction
- 5) Other safety/efficacy related information (influence upon clinical laboratory value, etc.)

2. Patient population

Women with serious deficiency of Luteinizing Hormone (LH) and Follicle-Stimulating Hormone (FSH) at less than 1.2 IU/L of endogenous serum LH

3. Sample size

A total of 600 cases or more shall be reported as per the number of report cases pursuant to the Paragraph 3 of Article 6 of the 'Re-examination Standards for New Drugs Etc.' (Ministry of Food and Drug Safety Notification No. 2014-61).

4. Study items

4.1 Basic information of subject

- 1) Date of birth

4.2 Medical history of subject

- 1) Concurrent disease
- 2) Allergic history

- 3) Period for infertility
- 4) Causes for infertility
 - ① Ovary factor
 - ② Cervical factor
 - ③ Uterine factor
 - ④ Oviduct factor
 - ⑤ Intra-abdominal abnormality
 - ⑥ Male infertility factor
 - ⑦ Immunological factor
 - ⑧ Unknown cause.
- 5) Previous ART experience
- 6) ART procedure
 - ① OI (Ovulation Induction)
 - ② IUI (Intra Uterine Insemination)
 - ③ IVF-ET (In Vitro Fertilization - Embryo Transfer)
 - ④ GIFT (Gamete Intra-Fallopian Transfer)
 - ⑤ ZIFT (Zygote Intra-Fallopian Transfer)
 - ⑥ ICSI (Intra Cytoplasmic Sperm Injection)
 - ⑦ Others

4.3 Indication for Pergoveris™

- 1) The levels of serum LH and FSH
- 2) The measured date of LH and FSH

4.4 Previous treatments for infertility

- 1) Presence or absence of previous treatment for infertility
- 2) The name and the administration cycle of drug (product) used

4.5 Current Pergoveris™ uses

- 1) Daily dose
- 2) Administration period: The administration start date and the administration end date

4.6 Concomitant medication

- 1) The name of concomitant medication (product)
- 2) Daily dose
- 3) Route of administration
 - ① PO (Per os)
 - ② IV (Intravenous)
 - ③ IM (Intramuscular)
 - ④ SC (Subcutaneous)
 - ⑤ SL (Sublingual)
 - ⑥ Ophthalmic
 - ⑦ TD (Transdermal)
 - ⑧ Others
- 4) Administration period: The administration start and end dates

4.7 Safety items

Adverse event (including side effect) and serious adverse event, including onset date, disappearance date, severity, causal relationship with Pergoveris™, measures on administration of Pergoveris™, and progress

4.8 Efficacy items

- 1) HCG administration
- 2) Follicular growth
- 3) Clinical pregnancy
- 4) Urine HCG test
- 5) Ultrasonography

5. Statistical methodology

5.1 Analysis dataset

5.1.1 Safety analysis dataset

Safety analysis will be conducted for all subjects who have been administered Pergoveris™ for at least once and followed up, except the following subjects.

- Subjects who have been treated Pergoveris™ before the contract

- Subjects with double enrollments
(If it is identified that the subject has been enrolled more than once at the same site, under the sponsor's confirmation, the one whose start date of Pergoveris™ administration is earlier will be selected and included for safety assessment.)
- Subjects who do not have any record of Pergoveris™ administration
- Subjects who administer Pergoveris™ for causes other than permitted usage

5.1.2 Efficacy analysis dataset

Among those subjects in safety analysis dataset, efficacy analysis will be conducted for subjects who have been evaluated for follicular growth after administration of Pergoveris™, except the following subjects.

- Subjects who were not assessed for follicular growth
- Subjects whose assessments of follicular growth were considered as 'undecidable'

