5.2 General principle

Continuous variables will be presented as descriptive statistics (mean with standard deviation, median, minimum and maximum values). For categorical variables, the number and percentage of subjects for each category and overall will be reported. Percentages will be based on the number of subjects observed at each category. All p-values will be presented as four decimal places. Values other than p-value such as mean, standard deviation, percentage, etc. will be presented as two decimal places.

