5.3 Handling of missing data

No imputation of missing data will be performed for statistical analysis except for administration start date and end date.

If only partial information of administration start date or end date is available and is required for calculation of administration period, total dose as well as the average daily dose, the following methods will be used.

- If day is missing, the day will be imputed as day 1.
- If month is missing, the month will be imputed as January.
- If year is missing, the date will be considered as missing.

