5.8 Efficacy evaluation

▪ **Follicular growth and clinical pregnancy**

- Follicular growth: The frequency and percentage of subjects who are thought to be 'effective' (at least one follicle in more than 17mm of mean diameter on ultrasonography) will be presented.
- Clinical pregnancy: For the subjects who underwent clinical pregnancy test (urine HCG test or ultrasonography), the frequency and percentage of subjects who are pregnant (urine HCG test 'Positive' or ultrasonography 'Yes') will be presented.

▪ **Factors that might affect the effectiveness in follicular growth**

The effectiveness in follicular growth for each factor of demographics (age) and baseline characteristics (concurrent disease, period for infertility, allergic history, previous assisted reproductive technology experience, luteinizing hormone, follicle stimulating hormone, previous treatments for infertility, concomitant medication), Pergoveris™ exposure (average daily dose, total duration, total dose) and special population (hepatic impairment, renal impairment) will be presented by the frequency and percentage. The effective rate for each factor will be analyzed using Pearson's chi-square test or Fisher's exact test.

Additionally, the effectiveness for all factors described above will be analyzed using multivariable

logistic regression.

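### Section 5.1.2 makes a decidable follicular assessment a condition for all efficacy analysis, so known pregnancy results drop out of the pregnancy rate

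*SAP*

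**What the plan says.** The SAP defines one efficacy dataset. Section 5.1.2 starts from the safety set and states that "efficacy analysis will be conducted for subjects who have been evaluated for follicular growth". It then lists two exclusions: "Subjects who were not assessed for follicular growth" and "Subjects whose assessments of follicular growth were considered as 'undecidable". Nothing there limits the rule to one endpoint.

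Section 4.8 lists the efficacy items, among them "3) Clinical pregnancy". Section 5.8, under efficacy evaluation, defines two outcome rates. One is the share of women with effective follicular growth. The other is clinical pregnancy, with its own condition: "For the subjects who underwent clinical pregnancy test (urine HCG test or ultrasonography"). For those women, "the frequency and percentage of subjects who are pregnant (urine HCG test 'Positive' or ultrasonography 'Yes') will be presented". Section 5.8 names no dataset for the pregnancy rate.

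Two general rules also apply. Section 5.2 says "Percentages will be based on the number of subjects observed at each category", and section 5.3 says "No imputation of missing data will be performed for statistical analysis except for administration start date and end date". In section 5.9, Appendix 2 reports how many women are in each dataset, how many are excluded, and the primary reason.

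**The concern.** Pregnancy is established by a urine test or an ultrasonography finding. Whether it is known does not depend on whether follicular growth could be judged. Section 5.1.2 nevertheless makes a usable follicular result the entry condition for every efficacy analysis. A woman can therefore have a complete pregnancy record and still be left out of the pregnancy percentage.

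Two things are at stake. Data already collected on an efficacy endpoint go unused, and the SAP gives no reason for it. The rate may also be shifted, because women without a decidable follicular result may differ from the others in their chance of pregnancy. The pregnancy rate is one of only two efficacy rates that section 5.8 defines, so it should not depend on whether the other one is available.

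**Working it through.** **No figure to reproduce.** The SAP gives no expected pregnancy rate, no expected share of unassessed or undecidable women, and no number tested. The 600 cases in section 3 are a regulatory reporting minimum, not the result of a precision or power calculation.

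**Step 1: the sections side by side.**
- 5.1.1: safety set.
- 5.1.2: safety set, restricted to women with a decidable follicular assessment, for efficacy analysis without qualification.
- 4.8 and 5.8: clinical pregnancy is an efficacy item, reported under efficacy evaluation.
- 5.8: a further condition, that a pregnancy test was done.

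The conditions nest: safety set, then decidable follicular result, then tested for pregnancy. The test condition in 5.8 adds to the restriction in 5.1.2 and does not lift it.

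**Step 2: effect on the rate.** All inputs here are assumptions.
- T = tested women in the safety set, taken as 500. The percentages do not depend on T.
- s = share of tested women without a decidable follicular result: 5%, 10% or 20%.
- p = pregnancy rate in the women kept: 30%.
- q = pregnancy rate in the women dropped: 0% to 60%.

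Rate reported under 5.1.2 = p. Rate in all tested women = (1 − s) × p + s × q. Difference = s × (p − q).

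For s = 10%, 450 women are kept, 135 of them pregnant (135/450 = 30.0%), and 50 known results are dropped:
- q = 0%: (135 + 0)/500 = 27.0%
- q = 20%: (135 + 10)/500 = 29.0%
- q = 30%: (135 + 15)/500 = 30.0%
- q = 60%: (135 + 30)/500 = 33.0%

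The other shares, by the same formula:

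| Share dropped | q = 0% | q = 30% | q = 60% |
|---|---|---|---|
| 5% | 28.5% | 30.0% | 31.5% |
| 10% | 27.0% | 30.0% | 33.0% |
| 20% | 24.0% | 30.0% | 36.0% |

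The reported 30.0% is too high if q is below p, too low if q is above p, and exact if they are equal.

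**Step 3: what the optional follicular figure would show.** Assume 80% effective among assessed women. Let m be the share of the safety set that is unassessed or undecidable. Counting those women as not effective gives 0.80 × (1 − m): 76.0% at m = 5%, 72.0% at 10% and 64.0% at 20%. These are lower bounds on a safety-set rate, not better estimates.

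**The case against.** The strongest reply is that section 5.8 gives pregnancy its own denominator, the women who were tested, and that the authors may have meant every tested woman in the safety set. That may have been the intention. The text does not say so: it names no dataset and makes no exception to 5.1.2. If that was the intention, the proposed sentence only records it.

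A second reply is that the effect may be negligible. The SAP does not show how many women would have a pregnancy result but no decidable follicular result, and equal rates give no shift. This stands. It limits the weight of the point, but it gives no reason for discarding the results.

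A reader might also infer something stronger: that both efficacy rates are faulty because they use only women with an observed outcome and no sensitivity rate is planned. The document does not support that as an error. Both denominators are stated openly, and not imputing outcomes is a declared rule. Section 5.2 plans numbers for each category and overall, and Appendix 2 reports exclusions with their primary reason, so the follicular lower bound can be rebuilt. The dummy-table annex is not shown and may display the untested women. The overall rates are descriptive, with no comparator or threshold. Nor can a reader conclude that the plan inflates the pregnancy rate, since nothing in the document fixes a direction.

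**Conclusion.** The point holds for the pregnancy rate. Section 5.1.2 as written excludes known pregnancy results because another endpoint is missing, and section 5.8 does not undo it. This rests on the wording alone and needs no numerical assumption.

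The size cannot be learned from the document. On the assumed inputs, with 30% pregnant among women kept and 0% to 60% among those dropped, the shift is at most 1.5 points either way at 5% dropped, 3 points at 10% and 6 points at 20%.

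Severity is minor. Safety is the primary objective (section 1), and the pregnancy rate is a descriptive percentage. The factor analyses in section 5.8 concern follicular growth only, so no test or model is affected.

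**What to change.** State in sections 5.1.2 and 5.8 that the follicular-assessment restriction applies to the follicular-growth analyses only. State that the pregnancy rate is computed among all safety-set women who had a urine HCG test or ultrasonography for pregnancy, and label that denominator in the table. If the narrower set is really intended, say so and give the reason.

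Optionally, show beside the planned follicular rate a labelled safety-set rate that counts unassessed and undecidable women as not effective, and show the number not tested for pregnancy. These additions are descriptive and do not correct an error. The safety set contains only women who were followed up, so the label should not call it all treated women.

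The cost is a few words of SAP text, with no new data. The two efficacy rates would rest on different denominators, which the tables must make clear. The optional follicular figure would be equal to or lower than the planned one and should be marked as a bound.

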5.2 General principle

Continuous variables will be presented as descriptive statistics (mean with standard deviation, median, minimum and maximum values). For categorical variables, the number and percentage of subjects for each category and overall will be reported. Percentages will be based on the number of subjects observed at each category. All p-values will be presented as four decimal places. Values other than p-value such as mean, standard deviation, percentage, etc. will be presented as two decimal places.

5.3 Handling of missing data

No imputation of missing data will be performed for statistical analysis except for administration start date and end date.

If only partial information of administration start date or end date is available and is required for calculation of administration period, total dose as well as the average daily dose, the following methods will be used.

- If day is missing, the day will be imputed as day 1.
- If month is missing, the month will be imputed as January.
- If year is missing, the date will be considered as missing.

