5.5 Pergoveris™ exposure

Pergoveris™ exposure will be analyzed as below.

- **Administration period**

Administration period is defined as the sum of each administration period and will be summarized as descriptive statistics. Also, the administration period will be classified as two levels (\leq median, $>$ median) and presented by the frequency and percentage for each level.

- **Total dose**

Total dose is defined as the sum of total doses on each administration period and will be summarized as descriptive statistics. Also, the total dose will be classified as two levels (\leq median, $>$ median) and presented by the frequency and percentage for each level.

- **Average daily dose**

Average daily dose is defined as total dose divided by administration period and will be summarized as descriptive statistics. Also, the average daily dose will be classified as two levels (\leq median, $>$ median) and presented by the frequency and percentage for each level.

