5.7 Safety evaluation

- **Occurrence of adverse event**

- For adverse event (AE), adverse drug reaction (ADR), unexpected adverse event (UAE) and serious adverse event (SAE), the total number of subjects, the number of events, the occurrence rate and 95% confidence interval will be summarized.
- AE and ADR will be classified by the system-organ class (SOC) and preferred term (PT) using WHOART (WHO Adverse Reactions Terminology) for nth investigation report and MedDRA (Medical Dictionary for Regulatory Activities) for re-examination report, and summarized by the number of subjects, the occurrence rate and the number of events.
- The details of unexpected adverse event, serious adverse event and adverse event of subjects who are excluded from safety evaluation in accordance with paragraph 5.1.1 will be listed.
- Severity, causal relationship, actions taken regarding Pergoveris™ administration and progress of AE categorized by SOC and PT using WHOART for nth investigation report and MedDRA for re-examination report will be analyzed by presenting the number of events and

percentage. If there are several levels for severity, causal relationship, actions taken regarding Pergoveris™ administration and progress of the same AEs, the level that will be used for the analysis will be the worst one on subject level.

▪ **Factors that might affect the safety evaluation**

The occurrence of adverse event for each factor of demographics (age), baseline characteristics (concurrent disease, period for infertility, allergic history, previous assisted reproductive technology experience, luteinizing hormone, follicle stimulating hormone, previous treatments for infertility, concomitant medication), Pergoveris™ exposure (average daily dose, total duration, total dose) and special population (hepatic impairment, renal impairment) will be presented by the frequency and rate with 95% confidence interval. The AE rate for each factor will be analyzed using Pearson's chi-square test or Fisher's exact test.

Additionally, the occurrence of adverse event for all factors described above will be analyzed using multivariable logistic regression.

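### Missing end dates are set to day 1 or January, as start dates are, with no check on their order, so administration periods can be zero, negative or far too long

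*SAP*

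**What the plan says.** Section 5.3 of the SAP opens with a general ban and one exception: "No imputation of missing data will be performed for statistical analysis except for administration start date and end date". When such a date is partial and is needed for administration period, total dose or average daily dose, the same rules serve both dates: "If day is missing, the day will be imputed as day 1" and "If month is missing, the month will be imputed as January". Only a missing year makes the date missing. There is no separate end-date rule, no condition on the order of the two dates, and no floor or fallback, either there or elsewhere in the SAP.

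Section 5.5 builds the exposure variables on these dates:
- "Administration period is defined as the sum of each administration period and will be summarized as descriptive statistics"
- "Total dose is defined as the sum of total doses on each administration period"
- "Average daily dose is defined as total dose divided by administration period"

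Each is described by mean, SD, median, minimum and maximum, and is split at its median. Section 5.7 uses them as factors for adverse events, with chi-square or Fisher tests, and adds that "the occurrence of adverse event for all factors described above will be analyzed using multivariable logistic regression". Section 5.8 does the same for follicular growth: "exposure (average daily dose, total duration, total dose) and special population (hepatic impairment, renal impairment) will be presented by the frequency and percentage". Total duration in those two sections is read here as the administration period of section 5.5.

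**The concern.** Replacing an unknown day by the first of the month pushes a date as early as it can go. For a start date this lengthens the course; for an end date it shortens it, often past the start. Four cases follow from the text:

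- **End day missing.** If start and end share a month and the start is not day 1, the period is zero or negative.
- **End month missing.** The end moves to January, on the recorded day if there is one. Unless the true end was in January, it usually lands before the start.
- **Start day missing.** The period is too long unless the true start was day 1.
- **Both days missing.** A course within one month becomes 1 day (0 if days are not counted inclusively).

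Period and total dose are then wrong in these records. Average daily dose is a ratio of the two, so for a single period at one daily dose the error cancels, except as 0/0 when the period is zero. It does not cancel when periods at different doses are summed. At stake are the exposure tables, where one record can produce a negative minimum, and the grouping of women in the factor analyses.

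**Working it through.** The SAP states no figure to reproduce. Its rules were applied to the calendar.

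**Inputs.** Date rules: SAP 5.3. Derived variables: SAP 5.5. Sample size 600, the stated minimum: SAP 3. Collected items are daily dose and start and end dates: SAP 4.5. Assumed: start dates spread evenly over four years (1,461 days); inclusive counting, period = end - start + 1; total dose = daily dose x days (5.5 gives no formula, but 5.3 says the dates are needed for total dose); course length; share of partial dates.

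**One record.** True course 10 to 19 March, 10 days.
- End day missing: 1 - 10 + 1 = -8 days.
- Start day missing: 19 - 1 + 1 = 19 days.
- Both days missing: 1 - 1 + 1 = 1 day.

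**End day missing, in general.** With true length D and true end on day d of the month, the imputed period is D - (d - 1). It is zero or negative when d > D. Over 48 months that is 1,461 - 48D days.

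| D (days) | Period <= 0 | Positive but too short | Correct (d = 1) |
|---|---|---|---|
| 5 | 1,221/1,461 = 83.6% | 13.1% | 3.3% |
| 10 | 981/1,461 = 67.1% | 29.6% | 3.3% |
| 14 | 789/1,461 = 54.0% | 42.7% | 3.3% |
| 21 | 453/1,461 = 31.0% | 65.7% | 3.3% |
| 28 | 117/1,461 = 8.0% | 88.7% | 3.3% |

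**End month missing.** If the day is known, the end moves back at least 31 days unless it was truly in January (124/1,461 = 8.5%). The period is therefore <= 0 in 91.5% for all lengths above. If the day is missing too, it is <= 0 in 98.6% (5 days) to 92.3% (28 days).

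**Start day missing.** The period is D + (start day - 1). The mean of day - 1 is 14.7, so a 10-day course averages 10 + 14.7 = 24.7 days, range 10 to 40.

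**Both days missing, 10-day course.** It stays within one month, and so becomes 1 day, in (1,461 - 9 x 48)/1,461 = 70.4%.

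**Two periods at different doses** (arbitrary units). 5 to 9 March at 1 per day, then 10 to 14 March at 2 per day with the second end day missing:
- Period: 5 + (-8) = -3, true value 10.
- Total dose: 5 + (-16) = -11, true value 15.
- Average daily dose: -11/-3 = 3.67, true value 1.50.

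**Study level.** Simulation with 600 women, courses uniform on 6 to 14 days, end day missing in a share p:

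| p | Mean | SD | Minimum (average) |
|---|---|---|---|
| 0 | 10.0 | 2.58 | 6 |
| 1% | 9.85 | 3.09 | -16 |
| 2% | 9.71 | 3.52 | -19 |
| 5% | 9.26 | 4.56 | -21 |

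The means agree with 10 - 14.7p to within rounding. The median was unchanged in about 94% of runs or more.

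**Wrong median group.** With median 10, 4/9 of women (11 to 14 days) belong in the upper group. A D-day course stays there only if the true end day is at most D - 10, that is 1 to 4 days per month, on average 2.5 x 48/1,461 = 8.2%. So 4/9 x 91.8% = 40.8% of affected women are misplaced; the simulation gave about 40 to 41%. Of all women, that is 0.4%, 0.8% or 2.0% at p = 1%, 2% or 5%. Counting women moved by an occasional shift of the median itself, it is about 0.5%, 1.0% or 2.6%. With the start day missing, about 50% of affected women are misplaced.

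**The case against.** The case for a lower rating is that the damage is confined and its extent unknown. Safety is the primary objective, and the adverse event, adverse drug reaction and serious adverse event rates do not use these dates. Neither do the follicular growth and pregnancy rates. Medians hardly change. The large percentages apply to each affected record, not to the study; with no partial dates the effect is nil, and data-management checks outside the SAP may exist. All of this stands and limits the size of the point. It does not rescue the rule: followed exactly, the plan yields impossible values at the analysis stage, after any data-entry check.

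Two further points also stand. The total-dose error rests on reading total dose as daily dose times days, which the SAP implies but does not write. And an order check alone would not be enough, because many end-day imputations give a period that is positive but too short (29.6% of affected 10-day courses, 65.7% at 21 days).

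On the remedy, it can be said that setting values to missing removes women from the multivariable models, so a net gain is not proven. That cost is real. But a partial date says too little about a short course to be imputed usefully, and leaving the value missing follows section 5.3's own general principle.

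**Conclusion.** The concern holds and should be fixed. That the rule can produce impossible periods follows from the text alone. How often it does so in an affected record depends on assumed course length: for end day missing, from 83.6% at 5 days to 8.0% at 28 days, with the right answer in only 3.3% at each length.

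The effect on the study cannot be sized, because the SAP gives no expected share of partial dates. Under the assumed 1% to 5%, the mean, SD and minimum of the exposure variables are visibly distorted, the median is nearly stable, and about 40% of affected women (about 50% if the start day is missing) enter the wrong exposure group. The consequences are limited to the summaries of section 5.5 and the exposure factors in sections 5.7 and 5.8.

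**What to change.** Delete the day-1 and January rules from section 5.3, together with the exception for administration dates in its opening sentence, since nothing would then be imputed. Replace them with text such as:

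> If the day or month of an administration start or end date is missing and cannot be resolved by query, administration period and total dose are set to missing. Average daily dose is kept only if a single constant daily dose is recorded; otherwise it is set to missing. If the end date is before the start date, all derived values are set to missing. The number of subjects affected is reported.

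The stricter treatment of reversed dates is deliberate: two complete dates in the wrong order point to a recording error in that record.

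Do not substitute a last-possible-day rule for the end date. It removes negative periods, but adds on average the same 14.7 days at the other end, so a 10-day course again averages 24.7 days.

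The cost is a few lines of SAP text and a small program change. Women with unresolved dates leave the period and total dose summaries and, because nothing else is imputed, the multivariable models that include these factors. Their number is unknown, which is why it should be reported.
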